- ^m Pharmacokinetic and ADA blood sampling will be taken prior to administration of study drug (pre-dose) on dosing days.
- ⁿ Administration of study drug should be done last after all study procedures unless indicated otherwise. Subjects will be monitored at the study site for at least one hour after study drug administrations at the following visits: for subjects enrolled to QW arms, on Day 1 and Weeks 1, 16, and 17; for subjects enrolled to Q2W arms, on Day 1 and Weeks 2, 16, and 18. After Week 4, qualified subjects may perform home dosing of study drug at weeks without study visits (see footnote a) and do not need to return to the clinical site on those weeks. Subjects may begin self-administration of study drug from Week 5 (QW dosing) or Week 6 (Q2W dosing). Subjects will be trained on study drug handling and self-administration of study drug at the study visits prior to beginning self-administration. A subject's caregiver or designee can also be trained on home dosing based on the subject's preference. Study-site staff will administer study drug at the first 2 visits. Thereafter, if home dosing is a consideration, the subject or subject's caregiver or designee must administer and demonstrate competency

for at least 2 visits prior to being allowed to dose at home. Otherwise, the subject will need to return to the site for all injections. The last dose of study drug for subjects dosed QW is Week 31 and for subjects dosed Q2W is Week 30.

[°] A dosing diary will be completed for every home dosing administration.

^p Subjects who end the study early will complete an early termination visit and complete the procedures described at the Week 32 visit within 2 weeks of the last dose of study drug.

2. Introduction

Izokibep is a potent and selective inhibitor of interleukin 17A (IL-17A) that is being developed for treatment of hidradenitis suppurativa (HS).

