7.3. Lost to Follow-up

A subject will be considered lost to follow-up if he/she repeatedly fails to return for scheduled visits and is unable to be contacted by the study site.

The following actions must be taken if a subject fails to return to the clinic for a required study visit:

- The site must attempt to contact the subject and reschedule the missed visit as soon as possible, counsel the subject on the importance of maintaining the assigned visit schedule and ascertain whether the subject wishes to and/or should continue in the study.
- Before a subject is deemed lost to follow-up, the investigator or designee must make every effort to regain contact with the subject (where possible, 3 telephone calls, and if necessary, a certified letter to the subject's last known mailing address or local equivalent methods). These contact attempts should be documented in the subject's medical record.
- Should the subject continue to be unreachable, he/she will be considered to have withdrawn from the study.

8. Study Assessments and Procedures

- Informed consent must be obtained before any study-related procedures are performed. In regions where the legal age of consent is older than 18 years, informed consent must be obtained from and signed by the subject.
- Study procedures and their timing are summarized in the SoA (Section 1.3). Protocol waivers or exemptions are not allowed.
- Day 1 corresponds to the date of the first dose of study drug.
- Visit/dosing windows of ±3 days on either side of the scheduled visits/dosing are permitted; however, the investigator should try to keep the subjects on the original visit/dosing schedule. The window of ± 3 days is relative to Day 1 and applicable for all subsequent visits/dosing. For QW dosing, the time between doses should be no less than 4 days and no more than 10 days. For Q2W dosing, the time between doses should be no less than 11 days and no more than 17 days.
- All assessments are to be completed before study drug administration, unless otherwise specified. It is recommended that patient-reported outcome assessments be completed first.
- Immediate safety concerns should be discussed with the sponsor immediately upon occurrence or awareness to determine if the subject should continue or discontinue study drug.
- Adherence to the study design requirements, including those specified in the SoA, is essential and required for study conduct.

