5.1. Time Points and Visit Windows

5.1.1. General Definitions

All assessment days will be related to the first day of the first dose of the study drug.

Day 1 is defined as the date of the first dose of the study drug. Relative days after Day 1 are calculated as (assessment date – Day 1 date) + 1. Relative days prior to Day 1 are calculated as (assessment date – Day 1 date). The day prior to Day 1 is Day -1. There is no Day 0.

The date of the first dose of study drug for each subject will be taken from the Study Drug Administration CRF page. If the date in this CRF page is missing, alternatively the date of enrollment/randomization will be used.

The date of the last dose of study drug for each subject will be taken from the Study Drug Administration form, with the last study drug administration date from any visit used as the date of last study drug.

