6.5. Measurements of Study Drug Compliance

Study Drug compliance is defined as the number of doses that were actually taken relative to the number of doses that should have been taken as per the protocol for the planned duration of treatment exposure. A partial dose in CRF will be treated as a half dose. Study drug compliance in Part B will be summarized for period 1 and period 2 separately.

In general, the percentage of overall compliance, assessed by dose count, will be calculated as follows:

For Part A

For Part B Period 1

For Part B Period 2

For Part A, the total number of doses expected to be administered from Week 0 to Week 31 is 32 for all subjects. For Part B, the total doses expected to be administered differs by treatment assignment: for QW dosing, the total doses expected to be administered is 16 for Period 1 and 16 for Part 2; for Q2W dosing, the total doses expected to be administered is 8 for Period 1 and 8 for Part 2.

The calculated percentage compliance will be categorized as:

- < 80% compliance
- $\geq 80\%$ compliance

Compliance will be summarized for the Safety Analysis Set for Part A (overall) and for Part B by treatment group and Period as follows:

- Number of doses will be presented by default summary statistics.
- Percent compliance will be presented by default summary statistics.
- Number and percentage of subjects within each of the compliance categories will be presented. Treatment compliance will be listed for the Safety Analysis Set. Missing data will not be imputed and only original data for those fields (for example, date fields) will be presented in the listing together with derived variables such as the calculated compliance (%) and exposure duration.

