To assess the pattern of initial onset, AESIs and ISRs will also be presented by Kaplan-Meier plot. This summary will be done for the full study period and, separately, only for Period 2. For the Period 2 summary, the day of onset will be calculated with respect to the Week 16 date of dosing (Date of AE - Date of Week 16 dose + 1).

Separate Kaplan Meier (KM) plots will be created for the study duration and Period 2 for time to:

- First onset of an event in each AESI category
 - If an AESI category has < 3 events in a treatment arm, then this analysis will not be done.
 - Subjects who do not experience an event will be censored at their date of last contact.
- First ISR
 - Subjects who do not experience an event will be censored at the date of their last injection.

The date/time of onset of the first instance of the event of interest (AESIs or ISRs) will be used as the date/time of the event in the analysis.

The product limit estimator will be presented by treatment group for Week 4 (Day 28), Week 8 (Day 56), Week 12 (Day 84), Week 16 (Day 112), Week 20 (Day 140), Week 24 (Day 168), Week 28 (Day 196), and Week 32 (Day 224) for each AESI category and for ISRs.

Incidence of ISRs will be summarized for the whole study period by treatment group, and injection visit week (Day 1, Week 1, Week 2, etc). If a subject didn't have an injection at the visit week, they will not be counted in the denominator for the incidence calculation.

A similar presentation of ISRs by treatment group and injection visit week will also be done, but the cumulative number of ISRs up to the injection visit week will be summarized at the visit week. This summary will be done for the full study period as well as by treatment period.

An overall summary of ISRs will be produced by treatment group, Period 1, Period 2, and for the full 32 week treatment period. The summary will include the number of subjects with:

- ISRs leading to discontinuation
- ISR at each maximum intensity/severity
- Related ISRs
- Serious ISRs
- Serious related ISRs

An ISR is considered to correspond to a particular visit week if it occurs on or after the indicated injection visit date/time, and prior to the next inject visit date/time. If no subsequent injection visit date/time is available, then the ISR will correspond to the closest injection visit date occurring prior to it.

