To evaluate the pattern of subjects experiencing multiple ISRs in Period 1 of the study (or the full treatment period in Part A), the number and percent of subjects with ISRs on or after Day 29 (through the end of the period) will be presented by the four treatment groups and by the following subgroups:

- Subjects who had at least one ISR on Days 1-28
- Subjects who had no ISRs on Days 1-28

A similar analysis by the four treatment groups will be presented for Period 2 Part B, where the two subgroups of interest are:

- Subjects who had at least one ISR up to Week 16
- Subjects who had no ISRs up to Week 16

ISRs will also be graphically presented by treatment group using a lasagna plot. The y-axis will be each injection visit week, the x-axis will represent each subject, and each 'square' on the plot will be color coded into the following categories: missing injection, no ISR at the visit, mild, moderate, and severe ISRs. The lasagna plot will be presented by treatment group, and sorted by ISR first onset and severity (earliest and most severe will be sorted at the top).

In addition, the following listings will be presented:

- Listing of Deaths
- Listing of TEAEs
- Listing of Serious TEAEs
- Listing of AEs Leading to Interruption of Study Treatment
- Listing of AEs Leading to Discontinuation of Study Treatment
- Listing of AEs of Special Interest

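### Time to first injection-site reaction: event-free subjects are censored on their last injection day while later reactions still count, so the Week 32 (Day 224) estimate has no event-free subject at risk

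*SAP*

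**What the plan says.** SAP 6.7.2 plans Kaplan-Meier plots for two kinds of event, over the whole study and separately for Period 2, with two censoring rules.

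- For adverse events of special interest (AESIs): "Subjects who do not experience an event will be censored at their date of last contact".
- For the first ISR: "Subjects who do not experience an event will be censored at the date of their last injection".

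The product-limit estimate is tabulated at eight timepoints from Week 4 (Day 28), the last of them "and Week 32 (Day 224) for each AESI category and for ISRs".

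On the event side, SAP 6.7.2 and Protocol 8.3.1 collect adverse events until 4 weeks after the last dose. SAP 6.7 includes events up to 28 days after the last dose received. SAP 6.7.2 assigns an ISR with no later injection to the closest preceding injection visit. A reaction that begins after the final injection is therefore a counted event.

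On dosing, the notes to the Schedule of Activities (Protocol 1.3) say "The last dose of study drug for subjects dosed QW is Week 31 and for subjects dosed Q2W is Week 30". The opening list of Protocol Section 8 adds "The window of ± 3 days is relative to Day 1 and applicable for all subsequent visits/dosing".

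**The concern.** A product-limit estimate needs the subjects in each denominator to be those in whom the event could have been seen on that day. Here the two sides use different windows. A subject who reacts after the final injection contributes an event on the day of the reaction. A subject watched over the same days without a reaction has already been removed. The follow-up after the final injection enters the numerator but not the denominator.

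The mismatch also applies to subjects who stop early, but while most of the arm is still being injected the risk set is large and the effect small. It bites at the end of dosing, when almost all event-free subjects leave within a few days, just before the last tabulated timepoint.

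ISRs were the most common izokibep-related event in the psoriasis trial (42 subjects, 38.9%; Protocol 2.2.3.3). A reader may well take the Week 32 figure as the cumulative ISR incidence on each regimen.

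**Working it through.** **Reproducing the plan's figures.** Week 32 as 7 × 32 gives Day 224, as stated. Weekly dosing at Weeks 0 to 31 gives 32 doses, which agrees with SAP 6.5 for Part A: "the total number of doses expected to be administered from Week 0 to Week 31 is 32 for all subjects".

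**Last day at risk, full-study clock.** SAP 5.1.1 sets the day count: "Relative days after Day 1 are calculated as (assessment date – Day 1 date) + 1". A dose at Week w falls nominally on Day 7w + 1.

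| Regimen | Last dose | Nominal day | Latest day (+3) | Gap to Day 224 |
|---|---|---|---|---|
| QW | Week 31 | 7 × 31 + 1 = 218 | 221 | 3 to 6 days |
| Q2W | Week 30 | 7 × 30 + 1 = 211 | 214 | 10 to 13 days |

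Every event-free subject dosed within window is censored before Day 224. This needs no assumption about reaction rates.

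**Effect of one late reaction.** The counts are assumed: a QW arm of 57, 22 early ISRs, 34 event-free completers last injected on Day 218, and one subject whose first ISR starts on Day 219.

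- Survival before Day 219: 35/57 = 0.614, a cumulative incidence of 38.6%.
- SAP rule: one subject at risk on Day 219 and one event, so 0.614 × (1 − 1/1) = 0. The curve shows 100%.
- If 5 of the 34 had their last injection on or after Day 219, six are at risk: 0.614 × 5/6 = 0.512, or 48.8%.
- Censoring at last injection + 28 days (Day 246): 35 at risk, so 0.614 × 34/35 = 34/57 = 0.596, or 40.4% (23/57), with 34 still at risk at Day 224.
- With no late reaction, the SAP rule carries 38.6% forward to Day 224 with nobody at risk.

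**Simulated size.** The inputs are assumptions: 1000 arms of 57 per regimen, 15% stopping early, ±3-day dosing windows, onset 0 to 3 days after injection, and ISR risk of 10% at each of the first four doses and 0.5% at each later dose.

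| Day 224 result | QW | Q2W |
|---|---|---|
| Event-free subjects at risk, maximum | 0 | 0 |
| Mean incidence, SAP rule | 46.2% | 41.0% |
| Mean incidence, censoring at +28 days | 42.9% | 37.8% |
| Arms showing 100% | 4.3% | 3.5% |
| Arms differing by more than 5 points | 7.9% | 6.4% |

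Other runs with onset 0 to 2 days and late per-dose risk of 0.2% to 1% gave a mean excess of 1 to 3 points, with 100% shown in 0.6% to 3% of arms. In a similar run with 12% risk at each of the first four doses, the median error at Day 224 was 0.3 to 0.7 points. At Week 28 the error averaged about 0.5 points, with a maximum of about 3.

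**Period 2 clock.** Counting the Week 16 dose as Day 1, the last injection is nominally Day 7 × 15 + 1 = 106 (QW) or 7 × 14 + 1 = 99 (Q2W). With the Week 16 dose 3 days early and the last dose 3 days late, these become Day 112 and Day 105. The tail of this curve has the same mismatch.

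**The case against.** The strongest defence is that the censoring date is deliberate: a subject is at risk of an ISR only while being injected, so follow-up should end with the last injection. The intention is reasonable, but the rule does not deliver it, because events after that date are not excluded. Excluding them would lose the reactions to the final injection.

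Other points limit the size, and they stand. Only the last of the eight timepoints is materially affected. The typical distortion is under a point, and the mean is pulled up by a few extreme arms. If reactions start on the day of injection and time is counted in whole days, censored subjects tie with the event and stay in its risk set; in simulation 100% then appeared in at most 0.3% of arms. The documents give no onset lag, late ISR risk or stopping rate. With no late reaction the Day 224 value is an unsupported carry-forward, not a wrong number.

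A reader might also infer more than the documents support:

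- **That the main tolerability outputs are compromised.** The Kaplan-Meier plot is an addition meant to show the pattern of initial onset. ISR summaries by period, by-visit incidence among those injected, cumulative counts, the severity and discontinuation summary and the lasagna plot do not use this censoring rule.
- **That nobody can be at risk at Day 112 in Period 2.** The SAP does not say that the listed timepoints apply on that clock, and a QW subject at the window extremes can just reach Day 112.
- **That the repeat-ISR table is wrong.** SAP 6.7.2 asks for "the number and percent of subjects with ISRs on or after Day 29 (through the end of the period"), split by ISR on Days 1 to 28, without requiring a later injection. It states no denominator, and SAP 6.1 lets the table shells, which are not in the documents, override the default. All treated subjects and those still being injected answer different legitimate questions.

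**Conclusion.** The inconsistency is real and follows from the SAP's own rules. Event-free subjects leave on their last injection day, later first ISRs remain events, and the tabulated Week 32 read lies 3 days or more beyond the last possible in-window injection on QW and 10 or more on Q2W. The empty event-free risk set at Day 224 rests only on in-window dosing.

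The numerical consequence rests on assumed onset lag, late risk and stopping rates. Under those tried, it is about 1 to 3 points on average at Day 224, usually less than one, with an occasional arm at or near 100%. The tail of the Period 2 curve shares the fault.

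This is a descriptive safety output, for which Protocol 9.3.5 rules out p-values. Alpha, power and all efficacy conclusions are unaffected. The correction is worth making because it is simple and the Week 32 figure is easily misread.

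**What to change.** In SAP 6.7.2, for time to first ISR:

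1. Censor event-free subjects at the earlier of last contact and 28 days after the last injection.
2. Count first ISRs over that same window, so that events and risk set agree. Adding only one dosing interval (7 or 14 days) to the censoring date would not be enough: ISRs starting after it would still count once event-free subjects had left, and the window would differ between regimens.
3. Apply the same rule to the Period 2 curve, state which timepoints are read on that clock, and report product-limit estimates only where subjects are at risk, with the number at risk shown.

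For completers on the nominal schedule, censoring moves to Day 246 (QW) or Day 239 (Q2W), so Day 224 becomes estimable. As an optional aid, the repeat-ISR table could show how many subjects in each subgroup had an injection on or after Day 29.

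The cost is a few sentences in the SAP and a programming change. No new data are needed, since adverse events are already collected for 4 weeks after the last dose.

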6.7.3. Laboratory Evaluations

Data for the following hematology, clinical chemistry, routine urinalysis, pregnancy testing, other screening tests, and other tests analytes received from the central laboratory are to be measured at the scheduled timepoints (Baseline, Week 4, 8, 12, 16, 24, 32, and 39).

Table 1 Laboratory Tests

Laboratory Tests	Parameters				
Hematology	Platelet count Red blood cell (RBC) count Hemoglobin Hematocrit	RBC indice Mean corpu (MCV) Mean corpu hemoglobin %Reticuloc	scular volume scular (MCH)	with Neu Lyn Mor Eosi	te blood cell (WBC) count a differential: trophils phocytes nocytes inophils ophils
Clinical chemistry1	Blood urea nitrogen (BUN)	Potassium	Aspartate aminotransfer (AST)/serum glutamic- oxaloacetic transaminase (SGOT)		Total and direct bilirubin
	Creatinine	Sodium	Alanine aminotransfer (ALT)/serum glutamic-pyru transaminase (SGPT)		Total protein
	Glucose (non-fasting)	Calcium	Alkaline phosphatase ₂		Fasting lipid (total cholesterol, triglycerides & HDL)
Routine urinalysis	 Specific gravity pH, glucose, protein, blood, ketones, by dipstick Microscopic examination (if blood or protein is abnormal) 				
Pregnancy testing Other screening tests	 Highly sensitive serum human chorionic gonadotropin (hCG) pregnancy test (as needed for women of childbearing potential) at screening Follicle-stimulating hormone and estradiol (as needed in women of nonchildbearing potential only) Serology hepatitis B surface antigen (HBsAg), and hepatitis C virus antibody Tuberculosis testing: QuantiFERON® test or purified protein derivative (PPD) test Note: T-SPOT® tuberculosis test may be acceptable if agreed upon with the medical monitor 				

In accordance with the baseline value definition in Section 5.1.2, the change from baseline will be derived as follows:

Change (unit) = (post-baseline value – baseline value)

All laboratory data will be reported in SI units. All quantitative laboratory test values at each assessed timepoints (Baseline, Week 4, 8, 12, 16, 24, 32, and 39) will be compared with the relevant reference range in SI units and categorized as:

- Low: Below the lower limit of the reference range.
- Normal: Within the reference range (upper and lower limits included).
- High: Above the upper limit of the reference range.

For summaries which present the worst value with respect to the reference range at the subject level, low and high are each chosen in preference to normal values. For parameters with both low and high reference ranges, subjects who have assessments within both low and high ranges will be counted within each category for worst value summary tables.

For analysis purposes, values preceded by a "<" or a ">" sign (i.e. those below or above the limits of quantification) will be considered equal to the lower or upper limit of quantification, respectively.

Laboratory data will be summarized by default descriptive summary statistics for continuous and categorical variables for the Safety Analysis Set:

- Observed values and change from baseline at each assessed timepoint (Week 4, 8, 12, 16, 24, 32, and 39) for each standard continuous laboratory parameter
- Number and percentage of subjects with categorized shift (low, normal, and high) values relative to the reference range at baseline compared to each post-baseline timepoint (Week 4, 8, 12, 16, 24, 32, and 39) for hematology and clinical chemistry
- Number and percentage of subjects with worst categorized (low, normal, and high) values relative to the reference range

Listings of all clinical laboratory data including derived change from baseline will be provided for the Safety Analysis Set. Within each listing, laboratory values outside the normal ranges will be flagged as either high or low.

6.7.3.1. Liver toxicity review

Potential liver toxicity will be assessed by listing subjects who met potential drug induced liver injury (DILI) criteria as described in the protocol and by summarizing subjects who met Hy's Law.

Subjects who met any (one or more) of the following criteria will be included in a listing for consideration of DILI:

- ALT or AST $\geq 5 \times ULN$ at any time
- ALT or AST \geq 3 x ULN at all (2 or more) assessments in a span of \geq 4 weeks
- ALT or AST \ge 3 x ULN and total bilirubin \ge 2 x ULN (>35% direct bilirubin) simultaneously at any time
- ALT or AST \geq 3 x ULN and international normalized ratio (INR) \geq 1.5 simultaneously at any time

- ALT or AST \ge 3 x ULN at any time during the study and weekly assessments after this finding are not available for at least 4 weeks
- ALT or AST ≥3 x ULN associated with symptoms (new or worsening) believed to be related to liver injury or hypersensitivity at any time

To determine subjects who meet the last criterion, a listing of all subjects who have at least one ALT or AST \geq 3 x ULN at any time, and who do not meet any of the first five criteria, will be reviewed by qualified medical professionals along with a listing of all AEs reported by such subjects. In coordination with the investigator, the medical professionals will assess whether any AE is believed to be related to liver injury or hypersensitivity and, if so, whether the elevated ALT or AST is in temporal association with the AE. Any subjects who meet these criteria will be included on a memo that will be filed in the TMF prior to database lock and unblinding, and included in the listings. For subjects who meet any of the six criteria, all LFT results at any time during the study will be listed, sorted by subject and date. Listing will include subject, treatment assignment, ALT, AST, bilirubin and INR, along with specific criterion met.

Subjects who meet the criteria for Hy's Law will be displayed in shift tables. Hy's Law is met when ALT or AST is $\ge 3 \times ULN$, total bilirubin $\ge 2 \times ULN$ and ALP is $< 2 \times ULN$, with all occurring simultaneously (at the same draw). At each assessment, subjects will be classified as meeting Hy's Law or not meeting Hy's Law. The shift tables will be presented as follows:

- Treatment period 1
 - Baseline (meet Hy's Law / not meet Hy's Law)
 - Any time during period 1 (meet Hy's Law at least one time / not meet Hy's Law at any time)
 - One table presented for each treatment arm (160 mg QW / 160 mg Q2W / combined placebo)
- Treatment period 2
 - Baseline prior to treatment period 1 (meet Hy's Law / not meet Hy's Law)
 - Any time during period 2 (meet Hy's Law at least one time / not meet Hy's Law at any time)
 - One table presented for each treatment arm (160 mg QW / 160 mg Q2W / placebo 160 mg QW / placebo 160 mg Q2W)

Separate Kaplan Meier (KM) analyses plots will be created for time to:

- First instance of meeting Hy's Law
- First instance of ALT or AST $\geq 5 \times ULN$
- First instance of ALT or AST \ge 3 x ULN and total bilirubin \ge 2 x ULN (>35% direct bilirubin) simultaneously

- First instance of ALT or AST \geq 3 x ULN and international normalized ratio (INR) \geq 1.5 simultaneously
- First instance of ALT or AST $\ge 3 \times ULN$ associated with symptoms (new or worsening) believed to be related to liver injury or hypersensitivity at any time

for the study duration (Day 1 through Week 32). In each plot, the subjects taking any treatment with Q2W frequency will be indicated by a solid line. The subjects taking any treatment with QW frequency will be indicated by a dashed line. Separate colors will be used to distinguish subjects randomized to izokibep and those randomized to placebo.

Subjects who do not experience an event will be censored at their last attended assessment. The date/time of onset of the first instance of the event of interest will be used as the date/time of the event in the analysis.

The product-limit estimator at Week 16 and Week 32 will be summarized by treatment group.

If there are < 3 events in a treatment arm for an event, then the KM analysis will not be done.

A listing of all LFT results from all subjects who meet Hy's Law at least one time during the study will be produced, sorted by subject and date. This listing will show subject, treatment assignment, period, ALT, AST, ALP, bilirubin and INR.

